- Cohort 1: Subjects from group 1 and group 2 will be scheduled for three study sessions as described below. A screening visit, an MR spectroscopy scan without hyperinsulinemic clamp (euglycemia) and an MR spectroscopy scan during a hyperinsulinemic clamp (hypoglycemia) with a tracer infusion.
- Cohort 2: Subjects from group 1 and group 2 will be scheduled for two study sessions. A screening visit as described below. An MR spectroscopy scan that will be conducted during a hyperinsulinemic clamp (combined eu- and hypoglycemia) together with a tracer infusion.
- Cohort 3: Subjects from group 1 and group 2 will be scheduled for two studysessions. A screening visit as described below. An MR spectroscopy scan conducted during a hyperinsulinemic clamp (combined eu- and hypoglycemia) without a tracerinfusion.
- Cohort 4: Healthy subjects from group 2 will be scheduled for one study session. They will undergo an MR spectroscopy scan without a hyperinsulinemic clamp nor any other i.v. infusions (i.e. no i.v. infusions at all).
- Cohort 5: Subjects from group 1 and group 2 will be scheduled for two studysessions. A screening visit as described below and a hyperinsulinemic clamp together with a non-labeled ketone or saline infusion without an MR spectroscopy scan.

Session A: Screening visit (YNHH Clinical Research Unit):

At the screening visit, study subjects in both the control and T1DM groups will complete the informed consent form for participation in voluntary clinical research. Demographic and clinical data collected will be reviewed by study personnel to confirm eligibility.

Once consented, all subjects will be further screened with a medical history & physical examination, blood work (electrolytes, hematocrit, creatinine, liver function tests and HbA1c) and a 12-lead electrocardiogram (EKG). Detailed subject inclusion and exclusion criteria are listed below (Human subjects – Subject recruitment). Subjects in the T1DM group only will be instructed to record their glucose readings to determine degree and frequency of hypoglycemia as described above. The subject will perform the preliminary cognitive tests at this point if they are selected for Cohort 5 at this point. The two subsequent MR sessions to complete the study will be scheduled at this point. The subject in the control group will have their two MR sessions scheduled without having to record any glucose readings.

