- 1. Type 1 diabetes mellitus of > 5 years (C-peptide negative age 18-60 years, on intensive insulin therapy (HbA1c <7.5%)
- 2. Non-diabetic volunteers, age 18-65 years that do not meet any of the exclusion criteria.

The following criteria will exclude subjects from study:

- 1. Pregnancy
- 2. Significant baseline anemia (hemoglobin <11.0 or hematocrit < 33%)
- 3. A history of liver cirrhosis or porto-caval shunt surgery.
- 4. Any contraindications for MRI scanning.
- 5. Subjects that follow a vegetarian diet
- 6. Subjects that exercise heavily on a regular basis (i.e. marathon runners)
- 7. Subjects with a history of anxiety/ panic attacks
- 9. How will **eligibility** be determined, and by whom?

Eligibility to participate in the study will be determined by [name]. Eligibility will be determined based on information collected at the screening visit after consent is obtained. This will include findings from physical examination, medical history, EKG, and laboratory testing in accordance with the inclusion and exclusion criteria listed above.

- 10. **Risks:** Describe the reasonably foreseeable risks, including risks to subject privacy, discomforts, or inconveniences associated with subjects participating in the research.
- 10.1. Intravenous catheters. The placement of intravenous catheters and/or the use of intravenous infusions can result in local hematoma formation or thrombophlebitis. Transient vasovagal symptoms including nausea, sweating, and lightheadedness may also occur during intravenous catheter placement.
- 10.2. Blood sampling. Same as above and frequent blood sampling may result in a drop in hematocrit.
- 10.3. Hyperinsulinemic hypoglycemic clamp technique. The hyperinsulinemic hypoglycemic clamp technique can result in hypoglycemia symptoms of varying severity. Subjects may experience autonomic symptoms including hunger, anxiety, tremor, palpitations, and/or diaphoresis. Others may experience fatigue, concentration difficulties, and/or mild confusion. The risk of plasma glucose levels falling below the target value of 50 ± 3 mg/dL is small but present; affected patients may experience exaggerated symptoms, as well as the development of dizziness, blurred vision, and/or confusion. All such symptoms would be rapidly reversible with an intravenous dextrose infusion.

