- 11. 11. Minimizing Risks: Describe the manner in which the above-mentioned risks will be minimized.

The primary risks to the subject are impact by magnetic objects accidentally brought into the magnet room, anxiousness, irritation due to the IV blood sampling, and hypoglycemia after the glucose infusion. The investigators in this protocol pioneered human infusion studies of stable isotope labeled metabolic substrates in MR systems and have been routinely performing these studies since 1988. Studies of brain metabolism using stable isotope infusion in the MRC have been performed since 1990. To date there have been no patient injuries during these studies and only minor adverse incidences (anxiety, IV irritation).

To confront the specific risks listed above:

- 11.1 Intravenous catheters will be placed under sterile conditions by experienced HRU staff members. All infused solutions will be prepared in sterile form by the YNHH pharmacy and will be tested for pyrogenicity and sterility prior to use. During dextrose infusions, 20% dextrose will be used to reduce the risk of thrombophlebitis normally associated with the use of excessively hypertonic glucose solutions.
- 11.2 No subject with a hematocrit less than 37% for males and less than 33% for females will be studied. All subjects having donated blood within 30 days of the study will be asked to postpone study participation (with a repeat blood count prior to future enrollment), and patients will be advised to refrain from blood donation for 30 days after each study completion. Total blood loss will not exceed half the amount of a regular blood donation for each study group. All blood losses will be replaced quantitatively with normal saline.
- 11.3 All study procedures, including the hyperinsulinemic clamp, will be performed under the direct supervision of a qualified, licensed practitioner.
- 11.4 No subject with a history of panic attacks will be enrolled in our study. To identify these subjects specific screening questions are administered during the screening visit. Licensed physicians and study nurses are present throughout the study to immediately recognize any distress subjects may experience. Studies would be immediately terminated should despite careful screening such an event still occur.

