At the screening visit, the participant will undergo the following assessments: physical examination with height and weight, medical history, blood draw for hematocrit, HbA1c levels, potassium, bicarbonate, creatinine, ALT/AST, lipid profile, ketones, and c-peptide. If female and of childbearing potential, a pregnancy test will be performed. Inclusion will be based on the above information and determined by the PI.

42. If yes, identify below all health information to be collected as part of screening and check off any of the following HIPAA identifiers to be collected and retained by the research team during this screening process.

Prior to the potential subject traveling to Yale for the screening visits, a collection of information concerning their eligibility will be done to help determine if they are eligible to be screened for inclusion. This will be done only to prevent unnecessary screening and travel for those who can be determined to be ineligible based on recognizable exclusion criteria. Through telephone correspondence, potential subjects will be asked the following information: Name, age, gender, date of birth, place of birth, race/ethnicity, address, phone number, height, weight, history of diabetes including treatment and complications, most recent HbA1c level, medications, history of other medical problems, history of claustrophobia, vegetarian, right/left handed, and previous studies at Yale. This information will be protected according to HIPPA policies and will be destroyed if the individual is determined to be not be eligible for the study during this telephone correspondence.

HEALTH INFORMATION TO BE COLLECTED:

HIPAA identifiers:
Names
All geographic subdivisions smaller than a State, including: street address, city, county, precinct, zip codes and
their equivalent geocodes, except for the initial three digits of a zip code if, according to the current publicly-available
data from the Bureau of the Census: (1) the geographic unit formed by combining all zip codes with the same three
initial digits contains more than 20,000 people, and (2) the initial three digits of a zip code for all such geographic
units containing 20,000 or fewer people is changed to 000.
☐ Telephone numbers
Fax numbers
⊠ E-mail addresses
Social Security numbers
Medical record numbers
Health plan beneficiary numbers
Account numbers
All elements of dates (except year) for dates related to an individual, including: birth date, admission date,

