Informed Consent	X	
Inclusion/Exclusion Check list	X	
Urine Pregnancy	X	X
(females)		
Blood Volume per visit	none	none

COHORT 5:

Schedule of Events:	Screening Visit Session A	Cognitive Testing Session D	Total Blood Collected
Informed Consent	X		
Medical History	X		
Physical Exam	X		
EKG	X		
Hematocrit (3 mLs)	X (3mLs)		
Creatinine (2 mLs)	X (2mLs)		
Liver Function Tests (3mLs)	X (3mLs)		
HbA1c (3mLs)	X (3mLs)		
Inclusion/Exclusion Check list	X		
Record Blood Sugar Levels 5x daily *	X		
Complete questionnaire for glucose readings <54mg/dl *	X		
Schedule cognitive testing session	X		
Urine Pregnancy (females)	X	X	
IV Placement		X	
Hypoglycemic Clamp		X	
Alternate Fuel (BHB) infusion		X	
Cognitive Testing	X	X	
Blood Volume per visit	11 ml	< 250ml	< 250 ml

^{*:} For diabetic subjects only

Any unused serum collected from all cohorts may be kept for additional metabolic studies or for confirmation of findings at a future time for both subject groups (non-diabetic and diabetic).

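### The exclusion list (Section V.8 item 2) sets one hematocrit limit of 33% for everyone, while Section V.11.2 bars men below 37%, and nothing says which limit governs for men

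*Combined protocol and SAP*

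**What the plan says.** Four places in the combined protocol and SAP bear on this point.

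- **Section V.8, exclusion item 2:** "Significant baseline anemia (hemoglobin <11.0 or hematocrit < 33", the last figure being a percentage. Sex is not mentioned.
- **Section V.9:** eligibility rests on screening findings, including "laboratory testing in accordance with the inclusion and exclusion criteria listed above". The list above it is V.8.
- **Section V.11.2:** "No subject with a hematocrit less than 37% for males and less than 33% for females will be studied".
- **Section V.10.2:** the risk that V.11.2 answers is that "frequent blood sampling may result in a drop in hematocrit".

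Section VII.4 includes hematocrit in the screening blood draw and then states: "Inclusion will be based on the above information and determined by the PI". The schedules of events list an item called "Inclusion/Exclusion Check list", but its content is not part of the documents. The recruitment text in Section VII.3 names significant anemia as an exclusion without giving a number.

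**The concern.** Two current sections give different numbers for the same screening test in the same people. V.8 is the list used to decide entry, and it carries the laxer male limit. A reader of V.8 has no cue that a stricter limit for men appears in the risk section.

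At stake is a participant-protection limit. Someone screening men from V.8 alone could accept one whom V.11.2 says will not be studied, and enrolling him would be a protocol deviation.

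**Working it through.** The protocol gives no calculated figure to reproduce. The check is a comparison of the two rules.

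**Inputs**

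- V.8 item 2: exclude if hemoglobin is below 11.0 or hematocrit is below 33%, either sex.
- V.11.2: do not study males below 37% or females below 33%.
- V.9: eligibility follows the V.8 list.

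**Size of the mismatch**

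- Men: 37 − 33 = 4 hematocrit points.
- Women: 33 − 33 = 0.

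**Outcome under each rule, for hemoglobin of at least 11.0**

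| Sex | Hematocrit | V.8 item 2 | V.11.2 | Agree? |
|---|---|---|---|---|
| Male | below 33% | excluded | barred | yes |
| Male | 33% to below 37% | passes | barred | **no** |
| Male | 37% or above | passes | passes | yes |
| Female | below 33% | excluded | barred | yes |
| Female | 33% or above | passes | passes | yes |

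Only one row disagrees. A man at 35%, for example, clears the anemia criterion in V.8 and is ruled out by V.11.2.

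**Does the hemoglobin limit close the gap?** It removes men below 11.0, so the affected men are those at 11.0 or above. It is not a documented backstop, however. The screening laboratory tests named in Session A (Section V.4), in Section VII.4 ("blood draw for hematocrit, HbA1c levels, potassium, bicarbonate, creatinine, ALT/AST, lipid profile, ketones, and c-peptide") and in the schedules of events include hematocrit but do not name hemoglobin.

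**Does any other text settle it?** V.9 points to V.8 alone. V.11.2 does not refer back to V.8. Section VII.4 leaves the decision to the principal investigator without stating a limit. No section says which male limit governs.

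**The case against.** The strongest reply is that the two rules are cumulative. V.11.2 is absolute, so passing V.8 does not by itself permit study, and anyone who applies the stricter limit complies with both. The principal investigator decides inclusion with the hematocrit result available, and the checklist may already carry 37% for men. A deviation follows only if someone works from V.8 alone. All of this stands, and it bounds the weight of the point. It does not remove the mismatch, because the protocol never tells the reader to apply the stricter number.

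A second reply is that entry conditions outside V.8 are normal in this protocol: the HYPO score, recent blood donation and claustrophobia also sit elsewhere. That is true, and location is not the fault. Those conditions add to V.8, whereas here both sections set a limit for the same test and the numbers differ.

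A third reply is that V.11.2 might be the text in error. The documents do not exclude this, so the fix asks for confirmation.

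Two stronger readings are tempting.

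- **Harm to the men affected.** A reader might infer that men between 33% and 37% would be endangered by the blood draw. The documents do not support this: both rules admit women at 33%, and the clamp visits carry the same bound of under 250 ml for all subjects.
- **An uncheckable limit in cohort 4.** A reader might infer this because that cohort's schedule shows no blood volume and no hematocrit row. But the Session A text in Section V.4 applies screening blood work, including hematocrit, to all subjects, and cohort 4 has no study draws for the limit to protect against. Any tension there lies between the Session A text and the cohort 4 schedule. That is a separate matter from the male limit.

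**Conclusion.** The point holds as a minor consistency error in a safety eligibility limit. V.8 item 2 and V.11.2 differ by 4 hematocrit points for men and agree for women. The men affected are those at 33% to below 37% with hemoglobin of at least 11.0. The documents do not say how many such men would present.

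The conclusion rests on two readings: that V.8 item 2, which is silent on sex, applies to both sexes, and that the criteria V.9 calls listed above are those of V.8. Both are the natural readings. The text mismatch is established. That anyone has been or would be wrongly enrolled is not, since the checklist is not available. No sample-size, power, alpha or analysis figure is affected.

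**What to change.** Change the hematocrit part of Section V.8 item 2 to below 37% for males and below 33% for females, leaving the hemoglobin limit as it is. This follows the stricter limit already stated. Have the sponsor confirm that 37% is the intended male limit; if it is not, correct V.11.2 so that both sections agree. Carry the confirmed limits into the inclusion/exclusion checklist.

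The cost is one line of protocol text, a confirmation and a check of the checklist. With the 37% limit, the only downside is possibly a few more male screen failures, all of them men whom V.11.2 already bars.

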To define the effect of alternate fuels on brain neurotransmitter metabolism in hypoglycemia unawareness we will compare its ability to modulate the oxidation of infused stable isotope-labeled glucose in healthy adults with that in age- and weight matched subjects with c-peptide-negative T1DM with a history of hypoglycemia unawareness. During clamped hypoglycemia all subjects will undergo an NMR spectroscopy scan that permits detection of the stable isotope used, which will be either carbon13 (¹³C) or deuterium (²H). Using isotopically labeled-glucose as a tracer together with a co-infusion of 350mM unlabeled lactate, we will measure neuronal glucose metabolite enrichment, visualize them in three dimensions and determine the time courses of enrichment. These will be fitted with our metabolic model to determine whether increased lactate stimulates PDH flux and glucose oxidation under hypoglycemia and to what degree this varies across different regions of the brain.

Subject Selection and Preparation:

Two groups of subjects aged 18-65 years will be studied:

- 1) Group 1 will be T1DM subjects (C-peptide negative, HbA1c <7.5%) with a history of severe hypoglycemia and hypoglycemia unawareness as assessed by the Ryan HYPO Score (see below) and as evidenced by interview, questionnaire and glucose log and/or continuous glucose monitoring.

- 2) Group 2 will be non-diabetic healthy subjects (fasting plasma glucose < 100 mg/dL, normal HbA1c) who are matched for age and gender to the type 1 diabetic subjects, to serve as controls for the study.

The Ryan HYPO score:

During a 4-week period subjects record blood sugar levels 5 times per day. On the occasion that the glucose recorded is <54 mg/dl subjects are asked to describe the details of the event using a questionnaire recently developed at Edmonton by Ryan et al. to more objectively define hypoglycemia severity. Particular emphasis in the questionnaire is devoted to the type of symptoms and whether help was required to

reverse the hypoglycemic event. From these data a composite HYPO score is generated based on the glucose readings and the patient's reported hypoglycemic events. A composite score in the upper quartile of T1DM control patients will be required for enrollment in this study.

Subjects will be placed into one of following cohorts:

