Non-diabetic control subjects will be asked to remain fasting from midnight prior to the study. Upon arrival to the MRRC, their blood glucose will be checked and an IV catheter will be inserted for infusion of insulin and glucose to maintain normal glucose levels and the study will ensue as described below.

For type 1 diabetic subjects receiving insulin via an insulin pump, they will be asked to check their blood glucose at home before bed and on awakening to ensure that the glucose level is above 70mg/dl and below 200mg/dl. They will be instructed to call [name] with any readings outside of this range. Upon arrival to the MRRC, their blood glucose will be checked as a safeguard, and insulin received via the insulin pump will be held. An IV catheter will be inserted for infusion of insulin and glucose to maintain normal glucose levels and the study will ensue as described below.

For type 1 diabetic subjects using multiple injections of insulin per day will be asked to ensure that the glucose level is above 70mg/dl and below 200mg/dl. As a safeguard, they

will be asked to check their blood glucose at home before bed and on awakening. Upon arrival to MRRC, their blood glucose will be checked; a nurse will place intravenous (IV) line to start infusions of glucose and insulin to maintain normal glucose levels.

At 9:00 AM on the day of this NMR session, a standard IV catheter will be inserted and used to deliver a continuous

MRS study design. After a set up period of approximately 30 minutes that includes a 1H MRS scan, subjects will be infused for 120minutes with the isotopic labeled substrate.

insulin infusion (2mU/kg/min) and a variable infusion of 20% dextrose. In addition a second IV line will be placed in the opposite arm to receive a normal saline solution and provide access for obtaining blood samples.

Once subjects arrive in the MR center they will be brought to a hypoglycemic state. The plasma glucose level will be gently lowered to 50 ± 3 mg/dL (see blood draw schedule below).

Once hypoglycemia is achieved tracer will be administered (see Figure above). Depending on the cohort assignment this will involve one of the following infusions:

 a) A 200mmol/l ¹³C /²H- alternate substrate infusion, which will be delivered through a port in the already-established IV site at a rate of 22μM/kg/min.

or

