- E. Can donor-subjects withdraw their materials at any time, and/or withdraw the identifiers that connect them to their materials?
 - i. How will requests to withdraw materials be handled (e.g., material no longer identified: that is, anonymized) or material destroyed)?
- **F.** Describe the provisions for protection of participant privacy
- **G.** Describe the methods for the security of storage and sharing of materials

6. **Statistical Considerations:** Describe the statistical analyses that support the study design.

Sample size calculations were performed using PASS 2002 (Hintze J. 2001. NCSS and PASS Number Cruncher Statistical Systems. Kaysville, Utah.). In our preliminary magnetic resonance spectroscopy experiments (see preliminary studies), under hypoglycemic conditions, we observed significantly greater fractions of glial oxidative metabolism supplied by acetate in T1DM subjects compared to non-diabetic controls $(0.19 \pm 0.066 \text{ vs } 0.10 \pm 0.020; \text{ a } 90\% \text{ increase in diabetics compared to controls})$. We will expect differences between severe hypoglycemia unaware and control subjects in this study to be on a similar scale. With a pooled standard deviation of 0.033, our proposed sample sizes (17 diabetic subjects and 17 non-diabetic controls) will provide 80% power at the two-sided 0.05 significance level to detect differences of 0.033 between diabetic subjects and non-diabetic controls representing a 33% increase from non-diabetic subjects. In short, we should easily have sufficient numbers of to address our primary endpoint of enhanced ketone body uptake and metabolism following recurrent hypoglycemia. Using this data, our proposed sample sizes of 17 subjects per group will provide >80% power to detect a 20% difference in the severe hypoglycemia unaware compared to each control group. We anticipate the changes seen will be much greater than that. Because small effects cannot be detected with sufficient power, conclusions based on failure to reject the null hypothesis will be avoided.

The same group size considerations apply to the cohorts studied with glucose/lactate coinfusions and the cognitive performance analysis under ketone infusion outside of the MRI scanners.

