e compounds will be sterility tested and certified to be free of pyrogens by the mpany. All certifications are kept in YNHH-IDS. YNHH-IDS prepares the study usion the day before the study and the study infusate is kept at 4°C.
 Use of Placebo: Not applicable to this research project If use of a placebo is planned, provide a justification which addresses the following: a. Describe the safety and efficacy of other available therapies. If there are no other available therapies, state this. b. State the maximum total length of time a participant may receive placebo while on the study. c. Address the greatest potential harm that may come to a participant as a result of receiving placebo. d. Describe the procedures that are in place to safeguard participants receiving placebo.
Use of Controlled Substances: Will this research project involve the use of controlled substances in human subjects? ☐ Yes ☐ No See HIC Application Instructions to view controlled substance listings.
If yes, is the use of the controlled substance considered: Therapeutic: The use of the controlled substance, within the context of the research, has the potential to benefit the research participant. Non-Therapeutic: Note, the use of a controlled substance in a non-therapeutic research study involving human subjects may require that the investigator obtain a Laboratory Research License. Examples include
ľ

APPROVED BY THE YALE UNIVERSITY IRB 3/4/2021

HIC#1208010648

controlled substances used for basic imaging, observation or biochemical studies or other non-therapeutic purposes. See Instructions for further information.

7.	7. Continuation of Drug Therapy After Study Closure Not applicable to this project Are subjects provided the opportunity to continue to receive the study drug(s) after the study has ended? Yes If yes, describe the conditions under which continued access to study drug(s) may apply as well as conditions for termination of such access.				
	☐ No If no, explain why this is acceptable.				
B.	DEVICES				
	1. Are there any investigational devices used or investigational procedures performed at YNHH, e.g., YNHH Operating Room or YNHH Heart and Vascular Center? Yes ☐ No ☒				
	SECTION VII: RECRUITMENT/CONSENT AND ASSENT PROCEDURES				
1. Ta	argeted Enrollment: Give the number of subjects:				
1	.1. targeted for enrollment at Yale for this protocol 100_				
1	12. if this is a multi-site study, give the total number of subjects targeted across all sites n/a _				

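### The 17-per-group size and its 80% power are extended to three analyses; on the natural reading that needs 102 completers, against an enrollment target of 100 that also supplies Cohorts 3 and 4

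*Combined protocol and SAP*

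**What the plan says.** Section V, item 6 (Statistical Considerations) states that "our proposed sample sizes (17 diabetic subjects and 17 non-diabetic controls) will provide 80% power" for a difference of 0.033 with a pooled SD of 0.033, two-sided 0.05. It then adds: "The same group size considerations apply to the cohorts studied with glucose/lactate coinfusions and the cognitive performance analysis" under ketone infusion. So one group size, with its power statement, covers three analyses.

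Section V, item 4 (Research Plan) says "Subjects will be placed into one of following cohorts" and lists five. For the tracer in Session C it says "Depending on the cohort assignment this will involve one of the following infusions": either a labeled alternate substrate, or labeled glucose with unlabeled lactate. Cohort 5 draws on both diagnostic groups and has "a hyperinsulinemic clamp together with a non-labeled ketone or saline infusion without an MR spectroscopy scan"; Session D describes how non-diabetic controls are prepared for it. Cohort 3 (both groups, clamp and scan without tracer) is additional, and so is Cohort 4: "Healthy subjects from group 2 will be scheduled for one study session".

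Section VII, item 1 gives the enrollment figure for the whole protocol: "targeted for enrollment at Yale for this protocol 100".

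Two places point elsewhere. Statistical Considerations appears a second time, as item 12 after the monitoring plan, without the sentence that extends the group size. Background section 2.1.5 describes the cognitive study in T1DM subjects only.

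**The concern.** A power statement made for one comparison is reused for two others, and the enrollment target does not clearly provide the subjects for all three. On the natural reading the three analyses alone slightly exceed the target, before anyone is placed in Cohort 3 or 4 and with no stated allowance for failed sessions. Something then has to fall below 17 per group, and the visible text does not say which analysis.

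At stake is whether the stated 80% power for a 1-SD difference is true of the glucose/lactate and cognitive analyses. A reader of those results would take the design to be sized for that difference when it may not be.

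**Working it through.** **1. The plan's own figure.** Inputs from Section V, item 6: difference 0.033, SD 0.033 (so d = 1), two-sided 0.05. For an unpaired t-test with n per group, df = 2n − 2 and the noncentrality is d·√(n/2). At n = 17, df = 32 and the noncentrality is √8.5 = 2.92, giving 80.7% power. The stated 80% at 17 per group reproduces.

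**2. Completers needed on the natural reading.** Three analyses × 2 groups × 17 = 102. Target: 100. Gap: 2.

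**3. What the gap alone does.** Spread over six groups, 100/6 = 16.67 per group gives 79.9% power, which rounds to the stated 80%.

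**4. What Cohorts 3 and 4 and losses do.** If the primary keeps 34, 100 − 34 = 66 remain. If k places go to Cohorts 3 and 4 or are lost, the other two analyses have (66 − k)/4 per group. The visible text gives no value for k, so these values are assumptions.

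| k (assumed) | n per group | Power for 1 SD | Detectable at 80% power |
|---|---|---|---|
| 2 | 16 | 78% | 1.02 SD |
| 6 | 15 | 75% | 1.06 SD |
| 10 | 14 | 72% | 1.10 SD |
| 26 | 10 | 56% | 1.32 SD |

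At 17 per group the detectable difference is 0.99 SD.

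**5. How the need changes with the reading.**

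| Reading | Subjects needed | Left of 100 |
|---|---|---|
| Repeated statistical section (item 12), which sizes one analysis only | 34 | 66 |
| Scanned subjects also do the cognitive session | 34 + 34 = 68 | 32 |
| Cognitive study in T1DM only (section 2.1.5) | 34 + 34 + 17 = 85 | 15 |
| One cohort per subject, controls in Cohort 5 | 34 + 34 + 34 = 102 | −2 |
| Ketone v saline between subjects, 17 per group per infusion | 34 + 34 + 68 = 136 | −36 |

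**6. The cognitive analysis may be paired.** The Research Plan describes two clamp occasions in random order, whereas the cohort list and the Cohort 5 schedule show one clamp session. If there are two occasions, the unpaired figures do not apply to ketone v saline. A paired t-test (df = n − 1, noncentrality dz·√n) at 80% power detects 0.72 SD of the within-subject difference with 17 subjects, 0.81 with 14 and 1.00 with 10.

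**7. At the plan's expected effect.** 0.19 − 0.10 = 0.09, and 0.09/0.033 = 2.73 SD: power exceeds 99.9% at 10 per group. If the quoted ± values are SDs, the pooled SD is √((0.066² + 0.020²)/2) = 0.049 and d = 1.85: power is 97% at 10 per group. This is an acetate measure; no expected effect is given for the lactate or cognitive outcomes.

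**The case against.** The document nowhere states 102. The figure needs three readings at once: the extending sentence means 34 new people for each analysis, nobody serves in two cohorts, and the cognitive comparison includes 17 controls. No text expressly bars a scanned subject from the cognitive session, and the repeated statistical section omits the extending sentence. The needs therefore run from 34 to 136. This stands, and it is why the point is conditional. The 102 reading is still the one that the cohort descriptions support most directly.

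The only gap that follows from the document's own figures is 2 subjects, which does not move power off 80% after rounding. This also stands. The lower figures rest on assumed use by Cohorts 3 and 4 and by losses. Figure 11A, titled as showing study groups, is not reproduced in the available text and may give sizes, so cohort sizes cannot be called absent from the plan.

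The plan expects a much larger effect than 1 SD, and it says it will avoid conclusions from non-significant results. Both limit the consequence, but the expected effect belongs to an acetate measure and does not carry over to lactate or cognition.

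A reader might take the payments as proof that nobody joins two cohorts: the recruitment text advertises up to $350, and the cheapest pair of cohorts would pay $60 + $300 = $360. That is weak. The $350 equals the Cohort 1 payment, and an advertised maximum for one participation does not rule out a second.

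**Conclusion.** The point holds in conditional form and is minor. With one cohort per subject and controls in Cohort 5, 17 per group in all three analyses needs 102 completers. The target of 100 cannot supply that together with Cohorts 3 and 4, so the extended group size is not delivered for every analysis. The loss of power is negligible from the gap of 2 alone. It reaches 72% at 14 per group and 56% at 10 only under assumed draws of 10 and 26 places.

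A reader might infer that the study is underpowered or must enrol more people. The documents do not support that: the primary comparison can keep 17+17 within the 100, several readings fit the target, and power at the plan's expected effect stays at 97% or more with 10 per group on the acetate measure. What fails is the blanket extension of one size and one power statement to the other two analyses.

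**What to change.** 1. Reconcile the two Statistical Considerations sections (items 6 and 12 of Section V), so that it is clear whether the group size extends beyond the first analysis.
2. Reconcile section 2.1.5, the Research Plan, the Cohort 5 description and the Cohort 5 schedule on the cognitive design: T1DM only or both groups, one session or two. State whether a scanned subject may also do the cognitive session.
3. Keep 17+17 for the primary ketone endpoint.
4. Replace the extending sentence with, for each other analysis, the n that the 100 allows once Cohorts 3 and 4 and losses are provided for, and the difference detectable at 80% power. Unpaired: 0.99 SD at 17 per group, 1.06 at 15, 1.10 at 14, 1.32 at 10. If cognition is a two-occasion comparison, use the paired values: 0.72 SD of the within-subject difference at 17 subjects, 0.81 at 14, 1.00 at 10.

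Cost: a text change and no extra patients. The downside is that the stated power of the non-primary analyses becomes less favourable.
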